During week 7 and at the beginning of week 9 of the intervention, participants will only receive the withdrawal symptom assessment. The actual content and structure of the behavioral therapy and tapering protocol will differ between the two groups, although the dose reduction schedule will be the same for the two groups (described below). Intervention sessions will take place in designated, private research rooms/offices at UCLA or at off-campus sites (VA West Los Angeles and Sepulveda campuses). All interventionist sessions (unless participant declined audio-recording during the informed consent process) will be audio-recorded and a random subset will be rated using a structured rating sheet to ensure fidelity to the treatment protocol. The interventionist will also maintain a session-by-session list of information covered and recommendations made. "Progress notes" will be maintained by the interventionist and reviewed during weekly "intervention meetings." These processes will ensure fidelity over the course of the study and avoid the risk of contamination across study arms.

Measures collected during intervention:

A urine sample will be collected from participants at the first intervention session. The urine sample will be tested by a licensed, accredited clinical laboratory (e.g., UCLA clinical lab) for benzodiazepines and zolpidem to confirm the participant's use/nonuse of these hypnotics.

The following measures will be collected weekly throughout the intervention for participants in both study groups.

Clinical Institute Withdrawal Assessment Scale - Benzodiazepines (CIWA-B): This 22-item instrument includes patient symptoms and clinical observations (e.g., tremor) to assess and monitor the type and severity of symptoms of benzodiazepine withdrawal.

Vital signs: These physical examination measurements will be taken weekly: blood pressure, pulse, and respiratory rate.

Insomnia Severity Index (ISI): The ISI is a 7-item instrument that measures perceived severity of insomnia symptoms (total score ranges from 0 to 28).

Epworth Sleepiness Scale (ESS): This 8-item questionnaire assesses general level of daytime sleepiness.

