If the participant is found to have mild symptoms of withdrawal based on select items from the CIWA-B or on mild changes in vital signs, the study physician (e.g., Drs. [name] or [name]) will be informed and the physician and the participant may decide to plateau the taper until the participant is ready to continue with the dose taper. If participants are found to have moderate, severe, or very severe scores on select items in the CIWA-B, moderate or severe vital sign changes, or have worsening severe insomnia, the study physician will be informed and she will discuss the patient's symptoms with a staff psychiatrist to determine whether changes to the taper schedule are needed (including increasing or plateauing the dose) and whether the patient needs additional clinical evaluation. If the patient needs immediate clinical evaluation, the participant will be escorted to the outpatient clinic or for life-threatening emergencies at our facility, we will call 911.

b) Hypnotic dosed as "prn" at baseline: Taper schedules for participants who used their hypnotic "as needed" at baseline will be adjusted so that the starting week's total weekly hypnotic dose does not exceed the participants' total weekly baseline hypnotic dose.

For the MTcap group, the capsules on the predetermined drug-free days will be filled with an inert filler substance. The participants will still be instructed to take the capsule on a scheduled basis nightly, not as needed. The use of inert capsules will ensure that the participant is not exposed to the drug more frequently than the baseline exposure. An increase in adherence to the taper protocol is one rationale for using capsules filled with inert filler substance rather than instructing participants not to take any capsule at all (i.e., similar to oral contraceptive inert pills that are provided in the monthly oral contraceptive pill pack). Another rationale for using inert capsules is related to our study's objective, which aims to develop an intervention for reducing placebo effects, such as the effects related to the conditioned response of taking the drug and attributing sleep and daytime function—which are known to vary from day to day—to the act of taking the pill.

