SGT+CBTI group: [name] or [name] will write prescriptions for the appropriate hypnotic that will cover the entire intervention period. The prescriptions will be sent via encrypted email or fax to the pharmacy. The compounding pharmacy will prepare a 30-day supply of the appropriate medication for the participant. The medication will be dispensed in a regular prescription bottle and labeled by the pharmacy. At the end of the month, a second 30-day supply of medication will be prepared and dispensed. The medication will be sent via overnight mail or courier to the UCLA Research Pharmacy. If necessary, the medications will be picked up by research staff and transported to the Research Pharmacy. The medication information will be entered into CareConnect (not as an active order) as “[medication name] study material Week [enter#]”.

Protocols for distribution of hypnotics

A chain of custody will be established and documented. Only authorized members of the research team will be permitted to have contact with the medications. A delegation log will be maintained. For both groups, a member of the research team will pick-up the medication bottle or blister packs from the UCLA Research Pharmacy upon arrival of the participant to the UCLA site and give it to the participant at the appropriate intervention session (for the SGT+CBTI group, at the initial session; for the MTcap group, at each intervention session). In the rare case that a participant reschedules the appointment after the medication has been dispensed, the medication will be temporarily stored in a safe. In the rare case that a patient withdraws from the study after the medications have been dispensed from the research pharmacy, the medication will be disposed of following US Drug Enforcement Agency Public Controlled Substance Safe Disposal protocol (e.g., in a DEA authorized collection bin, with two witnesses signing the chain of custody log).

For participants seen at off-campus sites, a research team member will transport the medication via personal car from the UCLA Research Pharmacy to the off-campus site. The medication will be placed in a locked bag and stored in the trunk during transport. The medication will be stored in a locked safe at the off-campus location until the participant receives it at the first session. If the participant does not come to the appointment, the medication will be returned to the safe.

Care coordination at end of intervention period

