Participants will receive up to \$150 for participation in the study. All enrolled participants will receive \$25 for completing the baseline assessment. Participants who are randomized will receive \$25 for the 2 hypnotic withdrawal assessments, and \$50 for the post-treatment assessment and \$50 for the 6-month assessment. Participants will receive payment even if they do not complete all components of an assessment. However, they will not be paid if they do not return the WatchPat or actigraph. Participants who go to UCLA Westwood for a study visit, will be given vouchers for parking fees associated with the UCLA Parking Structure (\$12/day).

Follow-up for Missed Appointments

Participants who miss a study appointment will be telephoned by research staff on the day of the missed appointment. If the participant does not return the call within 10 days of the missed appointment, a letter will be sent that encourages the participant to contact the research office (see Missed Appointment Letter). If a participant has not returned an actigraph or Watch-PAT device, the letter will also include a paragraph about the importance of returning the device and a reminder that the participant may be charged for any unreturned sleep devices (see Missed Appointment Letter). If the participant does not return the device after 10 days from the date of the first letter, a second letter

will be sent reminding participants that they may be charged for any unreturned sleep monitoring devices (see Failure to Return Device Letter).

Benefits and Risks

Potential direct benefits: Participants will learn techniques that could help them discontinue hypnotics and improve their sleep. It is possible that participants in this study may experience improved sleep quality following the intervention programs. Participants may also experience a reduction in the health risks associated with chronic hypnotic use (i.e., cognitive impairment, falls).

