Potential benefits to society: Hypnotic discontinuation is of critical importance to older adults. Clinical guidelines and professional groups recommend that older patients not be prescribed benzodiazepines and z-drugs, and in the context of insomnia, effective non-pharmacological treatments for insomnia are available. This study has the potential to boost hypnotic discontinuation rates. In addition, the study may provide new insight into the placebo effect. The ultimate goal of this line of research is to implement a program that can reduce hypnotic use long-term in older patients with current or past insomnia.

Potential risks/discomforts:

Benzodiazepine withdrawal symptoms: Symptoms are not common with withdrawal of low doses of benzodiazepines, but could include dizziness, anxiety, depression, and insomnia. The proposed intervention has a similar risk level to behavioral/ pharmacological strategies recommended by healthcare providers to adults as part of routine clinical care. Based on our pilot data and our team's collective clinical experience with low-dose hypnotic discontinuation, withdrawal symptoms that warrant protocol changes are uncommon. To reduce the risk of severe withdrawal symptoms, adults at high risk of complicated withdrawal or on high benzodiazepine doses (based on comorbidities, current prescriptions, and answers to assessment questions) will not be randomized to receive the intervention. Participants will be monitored weekly with the Clinical Institute Withdrawal Assessment-Benzodiazepine [CIWA-B] instrument and with weekly vital signs. If the participant is found to have mild symptoms of withdrawal based on select items from the CIWA-B or on mild changes in vital signs, a study physician (e.g., Drs. [name] or [name]) and the participant may decide to plateau the taper until the participant is ready to continue with the dose taper. If participants are found to have moderate, severe, or very severe scores on select items in the CIWA-B, moderate or severe vital sign changes, or have worsening severe insomnia, the study physicians will discuss the patient's symptoms with a staff psychiatrist to determine whether changes to the taper schedule are needed (including increasing or plateauing the dose) and whether the patient needs additional clinical evaluation. If the patient needs immediate clinical evaluation, the participant will be escorted to the outpatient clinic or for life-threatening emergencies at our facility, we will call 911.

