post-assessment and the six-month follow-up assessment. A courier will be sent to pick up the urine specimen and will deliver it to the UCLA lab in CHS that processes the research labs.

Six-month follow-up

Preparatory Emails

- (Auto-generated email): A reminder appointment will be created and invitation for 6-month follow-up appointment will be sent to the patient
- (Research staff-generated email)
 - Participants will be emailed a confirmation of their 6-month follow up visit appointment
 - Participants will be provided instructions for preparing for the 6-month follow up (e.g., anticipated duration, equipment/materials needed, staff contact information)

Getting Materials/Equipment to Participants

- Version for SIP Participants will be advised to pick up 6-month follow up visit 1 materials (in sealed envelopes) 1 day prior to 6-month follow up and to go to the lab to give urine sample (urine tox and urine zolpidem)
 - Diary
 - Questionnaire packet/instructions
 - Medication log
 - Wrist actigraph
 - Return Box
- Version for NIP Participants will be mailed 6-month follow up materials a few days before session 8
 - Diary
 - Questionnaire packet
 - Medication log
 - Wrist actigraph
 - Urine specimen containers
 - Postage-paid return, insured Return Box

A courier will be sent to pick up the urine specimen and will deliver it to the UCLA lab in CHS that processes the research labs.

Incentives for study participation

No changes.

Follow-up for Missed Appointments

No changes.

Benefits and Risks

no changes.

Primary data analysis plan and power analyses

No changes

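### The missed-appointment rule also covers weekly taper visits, yet its 10-day wait exceeds the promised 7-day withdrawal check and it states no notice to the study physician

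*Combined protocol and SAP*

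**What the plan says.** **The rule.** Under Follow-up for Missed Appointments, anyone who misses a study appointment "will be telephoned by research staff on the day of the missed appointment". Then: "If the participant does not return the call within 10 days of the missed appointment, a letter will be sent". The letter "encourages the participant to contact the research office". The remaining steps concern unreturned devices. The section does not distinguish taper visits from assessment visits. The addendum repeats the heading "Follow-up for Missed Appointments" and states that nothing changes.

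**The monitoring promise.** Measures collected during intervention introduces the CIWA-B and vital signs with "The following measures will be collected weekly throughout the intervention for participants in both study groups". The withdrawal-risk paragraph under Benefits and Risks states: "Participants will be monitored weekly with the Clinical Institute Withdrawal Assessment-Benzodiazepine [CIWA-B] instrument and with weekly vital signs". Modified taper plans continues weekly monitoring through an extended taper.

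**When the physician is involved.** Under Modified taper plans the trigger is a finding: "If the participant is found to have mild symptoms of withdrawal based on select items from the CIWA-B", or changes in vital signs, or more severe scores. The withdrawal-risk paragraph has the same structure.

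**Drug supply.** Protocols for distribution of hypnotics hands medication over at the initial session in SGT+CBTI and, "for the MTcap group, at each intervention session". SGT+CBTI receives a 30-day supply, then a second one. In both arms the participant's own bottle is bagged at the first session, with a label not to take it except on the study staff's instruction.

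**The concern.** Weekly CIWA-B and vital signs are the protocol's stated control for withdrawal during a taper of about 25% per week. The Risk/Benefit analysis relies partly on monitoring being more structured than in ordinary care. A no-show rule whose second step comes later than the next scheduled safety check weakens that control when followed exactly as written.

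The route to the physician begins with something found at an assessment. A participant who does not attend produces no finding, so the written procedure gives no reason to tell the physician. What is at stake is mainly safety oversight in both arms. For some in-person MTcap participants, continuity of study drug is at stake as well.

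**Working it through.** No sample-size or power formula applies. The check is calendar arithmetic plus a reading of the supply text.

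**Inputs**
- Monitoring interval: 7 days (Measures collected during intervention; Benefits and Risks).
- First step after a missed visit: a call the same day (Follow-up for Missed Appointments).
- Next step for that visit: a letter if the call is not returned within 10 days (same section).
- Assumptions: exact 7-day spacing, with the start of week 9 on day 56 and its end on day 62.

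**Monitoring gap**
1. Last completed check: day 0.
2. Missed weekly visit and call: day 0 + 7 = day 7.
3. Letter for that visit: day 7 + 10 = day 17.
4. Time since the last check: 17 days, against 7 promised. The excess is 17 − 7 = 10 days, and the ratio is 17 / 7 = 2.4.
5. The letter only invites contact, so 17 days is a minimum for someone who stays out of contact.
6. The next weekly visit, day 7 + 7 = day 14, falls inside the wait. If it too is missed, the same rule requires a call on day 14. Call attempts are then 7 days apart, but no check has been made.

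Going through the session table, the gap to the letter is 17 days for every contact from week 2 to the start of week 9. If only the end-of-week-9 visit is missed, it is 62 + 10 − 56 = 16 days.

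**Supply during the gap**

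| Participant | Effect of a missed visit on study drug |
|---|---|
| In-person MTcap, sessions one week apart, packs still containing drug | A 7-day pack covers nights 0 to 6. Nights 7 to 16 (10 nights) pass without a new pack before the letter, if no contact is made |
| In-person MTcap, monitoring-only visits (week 7, start of week 9) | None from the missed visit itself: packs are handed out at sessions |
| In-person MTcap, final pack | Little or none: it holds 4 placebo capsules and 3 empty blisters |
| Remote MTcap | None at once: several weeks of packs are held at home |
| SGT+CBTI | Exposed mainly at the second 30-day dispensing |

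**Other routes by which the physician might learn of an absence**
- Weekly intervention meetings review progress notes. The text does not say that a physician attends or that absences are raised.
- Primary care providers are told the final regimen. No timing is given for a participant who simply stops attending.

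**The case against.** The strongest reply is that the two sections do different jobs: one sets the schedule and the other handles no-shows. No schedule can examine someone who cannot be reached. Of the 17 days, 7 are the planned interval. The 10 days is when a letter backs up an unreturned call, and it does not bar staff from calling sooner. High doses, seizure disorder and high risk of complicated withdrawal are excluded, and the protocol expects withdrawal that warrants protocol changes to be uncommon. Escalation could also sit in working documents that are not public.

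Much of this is fair, and the sections are not in flat contradiction. But earlier calls are permitted rather than required, and the rule does not ask that any call cover symptoms. The protocol still relies on weekly checks as a safeguard despite the low expected risk.

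Three stronger readings are tempting and are not supported:
- *No contact attempt for 10 days after a single call.* A second missed weekly visit brings its own call on day 14.
- *A missed session leaves MTcap participants with no hypnotic at all, as an abrupt stop.* The bottle label allows use on staff instruction, and the supply gap is confined to the first row of the table.
- *The rule biases the arm comparison on drop-out or discontinuation.* SGT+CBTI has its own exposure at the second dispensing. The documents give no missed-visit rate from which to size an effect.

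**Conclusion.** The point stands as a gap between the no-show rule and the protocol's own safety monitoring, in both arms. A participant who stays out of contact during the taper can go at least 17 days without a CIWA-B or vital signs. No stated step in that time informs the study physician. The figure assumes weekly spacing, an unreturned first call and no check at the day-14 visit.

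The supply interruption is a secondary point, limited to in-person MTcap at early or middle sessions. The 10 nights is its size under those conditions and is not a general figure. No claim about treatment-effect bias is made. The point merits a protocol change but does not put the design in question.

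**What to change.** In Follow-up for Missed Appointments and in the addendum, separate taper-period visits (sessions and withdrawal checks) from assessment visits. For taper visits:
- have existing staff repeat contact attempts within the protocol's own weekly monitoring interval;
- offer the video or telephone visit already described in the addendum as a replacement. The addendum allows questionnaire items to be given verbally, but it lists a blood-pressure cuff only for remote participants, so say how vital signs are handled for others;
- make a missed withdrawal check known to the study physician.

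Keep the 10-day letter for assessments and unreturned devices.

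The sponsor must also reconcile the no-show rule with the weekly-monitoring and physician-involvement text, and with the pack hand-out and bottle-label text. No dose, supply or taper rule is proposed here. Those decisions stay with the sponsor and the study physicians.

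The cost is about one paragraph in the protocol and addendum, and a few extra calls by existing staff.
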